Aim 3 is intended to explore future implementation of the redeveloped TLC intervention with respite providers. This provides yet another layer of the tool's feasibility. We will host webinars to demonstrate the features and functionality of the TLC intervention as well as to preview pilot study results from Aim 2, then ask providers for feedback on their likelihood of implementation and barriers to using TLC with their clients.

Together, these three aims represent a comprehensive approach to Stage 1 research activities, with the overall goal of developing an intervention that is scalable to real world applications. Throughout all stages of the proposed project, our team is committed to community-engaged research practices, where community partners will provide input and connect us with potential research participants. Given this pragmatic yet scientifically rigorous approach, the results have the potential to guide and accelerate the eventual implementation of the TLC intervention to community and health care practice.

This application relates specifically to Phase 2 of the project, which specifically addresses Aim 2 where human subjects will be recruited and enrolled.

Study Population

Age of Participants: Over 18 years of age

Sample Size:

At Utah: 150
All Centers: 150

Inclusion Criteria:

Inclusion criteria:

AD/ADRD caregivers who are currently using or interested in using respite, such as home-care respite providers or adult daycare providers, or informally provided by family members or friends.

The caregiver must:

- 1) be the primary caregiver,
- 2) live in the same house with the care recipient,
- 3) have access to and/or interest in using respite at least once a week for a minimum of 4 hours,
- 4) be providing care to a family member with Alzheimer's disease or dementia,
- 5) be English speaking, and
- 6) be age 18 or over.

We will recruit a total of 150 caregivers with purposive selection of caregivers to ensure that we are getting a diverse sample of caregivers (i.e., males and females, racial and ethnic diversity, rural and urban residence, early and late-stage dementia caregivers).

Exclusion Criteria:

- Not a primary caregiver
- Not living in the same house with the care recipient
- No access and/or interest in using respite at least once a week for a minimum of 4 hours
- <18 years of age
- Non-English speaking
- Not providing care to a family member with Alzheimer's disease or dementia

Design

Randomized Trial

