Because this is part of early-stage intervention development activities (Stage 1), we have designed a clinical trial to pilot-test feasibility as well as efficacy of the redeveloped TLC intervention. We propose to use a waitlist control cohort design, using a fully powered sample to provide the most rigorous analysis possible. The waitlist design allows all participants to receive the intervention. As shown here in the figure, participants will be randomized to one of two sequences. After baseline data collection and an initial orientation/control period for the first 4 weeks, Group A will have 8 weeks of TLC intervention, then 8 weeks of follow-up. Group B will have 8 weeks of waitlist control, and then TLC intervention for 8 weeks, beginning at week 12. We will use ecological momentary assessment (EMA) during the entire 20-week study period to capture daily time-use trends for any respite periods received (n=140 daily reports, max). EMA aims to minimize recall bias and maximize ecological validity. Primary outcomes data will be collected via electronically administered surveys at baseline (T0) and every 4 weeks thereafter (T4, T8, T12, T16, T20), for a total of 6 assessments. This randomized, prospective, and longitudinal design

allows each participant to serve as its own control and offers opportunities to assess both within- and between-group differences over time (Group A vs. B).

Measures

The primary outcome is wellbeing, measured with two standardized scales indicating “caregiver burden” and “anxiety.” The mechanism driving the intervention effect is theorized to be related to respite time-use and time-use satisfaction. This construct is measured with “experienced” and “evaluative” time-use measures.

Analysis

The analysis to test for efficacy will specifically look at treatment x time interaction that combines both vertical (between individuals at given timepoints) as well as horizontal (evolution within individual over time) comparisons. We will utilize a multilevel model that consists of level 1 (within person) and level 2 (between person). Thus, the overall composite two level Multi-Level Mixed effects Model (MLM) is defined as follows with the first set of brackets representing fixed effects and second set random effects:

$$Y_{ij} = [\beta_0 + \beta_1 T_j + \beta_2 X_{ij}] + [\zeta_{0i} + \zeta_{1i} T_{ij} + \epsilon_{ij}] \quad [\text{equation 1}]$$

[figure not shown]

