Time-use satisfaction data will be collected daily using EMA, of short questions. First, did you have respite today? Then, if yes, how satisfied are you with your respite time-use? (1-

5) Did the respite time make you feel more positive/negative about your role as a caregiver? (1-5). These two items measure “experienced” and “evaluative” time-use measures, respectively, which have been theorized to be associated with the wellbeing outcomes (anxiety & caregiver burden). Aggregated averages of these two measures will be computed for specific time-periods (i.e., across the four-week interval spanning the primary data collection timepoints). The same MLM will test significance of time x intervention interaction on mean Time-use satisfaction following TLC intervention compared to WLC.

H3: Higher time-use satisfaction will be associated with lower burden & anxiety (direct effect)

Using the same MLM framework, we will examine if aggregate Time-Use Satisfaction (predictor) is associated with lower “caregiver burden” and “anxiety.” As an exploratory aim we will examine Time (β_1) immediately post intervention through follow up to determine maintenance, attenuation, or no change in Group A outcomes after TLC for wellbeing (anxiety & caregiver burden) and time-use satisfaction (experienced & evaluative time-use).

Figure 3: Time-use mediates TLC impact on Well Being

H4: Higher time-use satisfaction will mediate the effect of the intervention on burden and anxiety (direct & indirect effects)

Figure 3 displays our overall mediation model, whereby TLC intervention improves wellbeing by increasing Respite Time-Use Satisfaction. We hypothesize that “satisfaction with respite time-use” is the factor that links respite use with wellbeing outcomes such that TLC intervention leads to improvements in respite quality that in turn produces better outcomes over time.

Mediation analysis will be conducted as previously outlined for cross-sectional as longitudinal models.^{149, 138, 139} In its simplest form, mediation is represented by three linear equations

$$\text{Mediator (Time-Use)} = i1 + aX + e1 \quad (2)$$

$$Y (\text{Wellbeing}) = i2 + cX + e2 \quad [\text{without mediator}] \quad (3)$$

$$Y (\text{Wellbeing}) = i3 + c'X + bM + e2 \quad [\text{with mediator}] \quad (4)$$

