Feasibility

All three aims of the overall project have a shared goal of evaluating some aspect of the intervention's feasibility. This is not a hypothesis driven analysis, other than we expect that the TLC intervention to be feasible, from the perspective of both caregiver and provider. Our goal is to gather rich data to describe how the intervention is or is not feasible, and how it might be improved in later steps toward eventual implementation.

To guide the feasibility-related analyses, we plan to use the five dimensions of the widely-accepted and NIH-endorsed RE-AIM framework (Reach, Efficacy, Adoption, Implementation,

Maintenance).141-145 RE-AIM provides a systematic and standardized way to think about feasibility, and to improve the sustainable adoption and implementation of evidence-based interventions. To assess for overall feasibility, the Investigators (PI [name] & Co-I [name]) will systematically archive whether the intervention achieves RE-AIM metrics during each phase of the project. Some of these measures are quantifiable and will be evaluated using statistics (primarily descriptive statistics); others will rely on qualitative metrics.

First, we present an overview of the feasibility indicators we plan to use in the study, along with descriptive benchmarks that would indicate high levels of feasibility on any given item (Figure 4). Second, we present an overview of the RE-AIM framework, noting which types of data and/or analyses from the proposed study will be used to illustrate each of the five dimensions of RE-AIM (Figure 5). These frameworks provide a structure and systematical methodology for us to consider as we explore and analyze the quantitative and qualitative measures of feasibility across the three phases of the study.

Figure 4. Quantifiable Feasibility Indicators and Benchmarks

Research Feasibility	Benchmark
Length of time to identify potential participants (by recruitment sources)	12 months
Consent/Enrollment Rate vs. those eligible	$\geq 50\%$
Enrollment rate (participants/month)	$\geq 12/\text{month}$
Research design-related dropout rate	$\leq 10\%$
Data collection completion rates (Primary data points and EMAs)	$\geq 80\%$

Feasibility	Benchmark
Access to computer & internet	$\geq 90\%$
Length of time to finalize web page design for testing	24 months
Length of time to hire and train hotline/chat line staff	3 months
System fail rate (e.g., system crashes, down server)	$\leq 5\%$
Dosage (# of log-ins)	At least 1/week

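### H2 to H4 use a plain four-week average of respite-day satisfaction ratings with no allowance for how many ratings it holds; this can dilute the mediation path and wastes some precision for H2

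*Combined protocol and SAP*

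**What the plan says.** The H2 section describes the daily assessment: "First, did you have respite today? Then, if yes, how satisfied are you with your respite time-use" (scored 1 to 5). A second 1-to-5 item follows, so each of the two satisfaction measures is a single item that exists only on days with respite.

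The ratings are then reduced: "Aggregated averages of these two measures will be computed for specific time-periods", namely "across the four-week interval spanning the primary data collection timepoints". The same mean serves three purposes:

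- **H2:** it is the outcome in the two-level mixed model.
- **H3:** it is the predictor: "Using the same MLM framework, we will examine if aggregate Time-Use Satisfaction (predictor) is associated with lower" burden and anxiety.
- **H4:** it is M in equations 2 to 4. The product a×b is tested with the Sobel test, and full mediation is declared if the treatment coefficient loses significance once M is in the model.

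The documents do not forecast the number of ratings. Inclusion criterion 3 asks caregivers to "have access to and/or interest in using respite at least once a week for a minimum of 4 hours". The Study Design section gives a ceiling of "n=140 daily reports, max" over 20 weeks. Figure 4 sets a benchmark of at least 80% for "Data collection completion rates (Primary data points and EMAs").

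**The concern.** An average of two ratings is a noisier measure of a caregiver's satisfaction than an average of fifteen, yet both enter the models alike. No section sets a minimum count, weights by count, adds a day level to the two-level model or corrects for unreliability.

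The safeguards that are present deal with other problems. Bootstrapping and the non-normality tests address the sampling distribution of a×b. Proration and the 30% rule in the Missing Data section address unanswered scale items. Maximum likelihood and multiple imputation address absent values, not noise in an observed mean.

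For an outcome (H2), such noise costs precision. For a predictor or mediator (H3, H4), it biases the coefficient. At stake is how the treatment effect is divided between the satisfaction pathway and everything else, which is the question H4 asks.

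**Working it through.** **The plan's own figure.** The only related number is the mediation power: above 80% for 75 to 120 participants with medium paths. Medium is not given a value. If it is assumed to be 0.39 per path, simulated Sobel power is 0.69 at 75, 0.82 at 90 and 0.945 at 120; at 0.30 it is 0.64 at 120. Without a definition the figure can be neither confirmed nor refuted, and the point below does not depend on it.

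**Inputs.**
- Ratings per interval, k: not stated. Once a week gives about 4 in four weeks, but this is a floor on access or interest, not expected use. The ceiling is 140 / 20 × 4 = 28. Four respite days at 80% completion give 3.2 ratings.
- ICC of a single rating (share of its variance that is stable over the interval): not stated. Assumed 0.27 to 0.50, with 0.1 to 0.7 as a wider range.

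**Step 1: reliability of the mean.** λ = k×ICC / (1 + (k−1)×ICC).

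| k | ICC 0.27 | ICC 0.50 | Loss, 1−λ |
|---|---|---|---|
| 3.2 | 0.864/1.594 = 0.54 | 1.6/2.1 = 0.76 | 24 to 46% |
| 4 | 1.08/1.81 = 0.60 | 2/2.5 = 0.80 | 20 to 40% |
| 12 | 3.24/3.97 = 0.82 | 6/6.5 = 0.92 | 8 to 18% |

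At k = 4, the wider ICC range gives a loss of 10% (ICC 0.7: 2.8/3.1 = 0.90) to 69% (ICC 0.1: 0.4/1.3 = 0.31).

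**Step 2: effect on equations 2 to 4.** With random error in M that is unrelated to arm, a is unchanged, b becomes λ×b, a×b becomes λ×a×b, and c' becomes c' + (1−λ)×a×b. Take a = b = 0.39 and c' = 0 as an illustration, so a×b = 0.152:

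- λ = 0.80: expected a×b = 0.122 and c' = 0.030; simulated 0.122 and 0.031.
- λ = 0.60: expected 0.091 and 0.061; simulated 0.092 and 0.062.

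A spurious direct effect appears, which works against a rule that needs c' to be non-significant.

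**Step 3: the mixed model.** H3 uses the mixed model, not one record per person. A small check (random intercept only, 120 people by 5 intervals, 40 runs per setting, four ratings) gave a fall in b of 26 to 46% at total reliability 0.80 and 52 to 59% at 0.63. It was about 73% at total reliability 0.80 when almost all true variance lay between people. Within-person reliability is below λ, so Step 1 can understate the loss here.

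**Step 4: H2 precision.** Set the single-rating variance to 1, so a mean of k ratings has variance v = ICC + (1−ICC)/k. Treating intervals as independent, for simplicity, equal weighting has R = mean(v) × mean(1/v) times the variance of optimal weighting. The share that weighting would remove is 1 − 1/R.

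- Counts even over 1 to 4: R = 0.6502 × 1.6832 = 1.094 (ICC 0.27) and 0.7604 × 1.3583 = 1.033 (ICC 0.50), so 9% and 3%.
- Counts even over 1 to 20: R = 0.4013 × 2.7143 = 1.089 and 0.5899 × 1.7355 = 1.024, so 8% and 2%.
- Very uneven, ICC 0.27: half the intervals with 1 rating and half with 16 give R = 0.6578 × 2.0842 = 1.371, so 27%; with 1 and 20, R = 0.6532 × 2.1313 = 1.392, so 28%.

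**The case against.** **The target may not be a latent mean.** The Study Design section says the daily assessments capture the respite periods received. If the mediator is satisfaction with the respite that took place, four rated days out of four are a near-census, day-to-day differences are real, and most sampling error disappears. A latent-mean correction could then overstate b. This stands as a condition on the finding. It is not a full answer: the plan also calls satisfaction a construct and the theorised mechanism, and the error of a single item and unrated respite days would remain.

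**Stronger readings that the documents do not support.**
- A reader might take 20 to 40% as the expected bias. It is not: neither the ICC nor the number of ratings is given.
- A reader might infer that mediation power falls well below the stated level. That needs a numeric medium path and the premise that it is on an error-free scale. If the planned effects describe the observed average, stated power is not reduced.
- A reader might conclude that H3 and H4 are biased against the mechanism overall. Mediator and outcome are both self-reported by the same caregiver, so shared reporting error or confounding could push b upwards. The net direction is unknown.

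**Scope.** Equations 2 to 4 are described as the simplest form, and the longitudinal version follows references not reproduced in the plan, so the absence of a correction is read from silence. H1 is untouched, and the plan describes the efficacy and mechanism hypotheses as exploratory. These points limit the importance of the finding but do not remove it.

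**Conclusion.** The point holds in conditional form, as a cheap improvement. The plan averages respite-day ratings and ignores their number.

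If the target is underlying satisfaction in the interval and rating error is random and unrelated to arm, measurement error alone biases b and a×b towards zero and moves the loss into c'. In single-level equations 2 to 4 the loss is about 20 to 40% with four ratings and 8 to 18% with twelve, both at an assumed ICC of 0.27 to 0.50. It may be larger for within-person mixed-model estimates. It is small if nearly all respite days are rated and the respite that occurred is the target.

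For H2 the cost is precision only: roughly 2 to 9% of variance for evenly spread counts and about 27 to 28% for very uneven ones. No claim about lost power follows.

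**What to change.** - **H2:** fit the daily ratings directly in a mixed model (days within four-week interval within caregiver), so that each interval is weighted by its number of ratings.
- **H3 and H4:** keep the planned average as the main analysis. Add a prespecified sensitivity analysis that corrects b, a×b and c' for the reliability estimated from within-interval variance, or that uses latent interval means if the model converges. Latent means should not be the main analysis: with about 120 caregivers and few ratings per interval, they trade bias for variance and change the target.
- **Target:** state whether it is underlying satisfaction or satisfaction with the respite that occurred.
- **Reporting:** give the number of ratings per interval by arm, and do not base the full-mediation statement on the uncorrected c' alone.

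No new data are needed. The cost is more analysis work, wider intervals for the corrected estimates, and possible instability if many intervals hold one rating, since these carry no information on within-interval variance.

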Participants are also asked to complete daily ecological momentary assessments (EMAs), in which they indicate if they used respite that day, and if so, their experienced and evaluative satisfaction with respite time-use. The daily EMAs will take about 1-2 minutes to complete as they are only 3 items (respite used [yes/no], and two items each measuring experienced and evaluative time-use satisfaction). The caregivers will be prompted weekly to complete their EMAs. Note: as mentioned above, all EMA data collection has been

integrated into the online version of the TLC intervention tools through a digital calendar, combining the TLC intervention with the collection of daily EMA.

Each questionnaire will take about 10-45 minutes to complete. The baseline and final questionnaire are significantly longer than the monthly questionnaires (i.e., 10 minutes versus 45 minutes). Questionnaires will include standardized fixed-choice and open-ended survey questions related to :

- demographic indicators
- caregiving context, and
- caregiver health and well-being (i.e., burden, anxiety, positive affect, global health).

The final questionnaire includes additional measures related to the participants' use of the TLC intervention tools. We will assess their perceptions of feasibility, usability, and acceptability of the online version of the TLC intervention. Other feasibility indicators such as login behavior, intervention protocol completion, and dosage will be imported in real-time directly from google analytics into the secure REDCap data base.

Procedures performed for research purposes only:

[figure not shown]
Statistical Methods, Data Analysis and Interpretation

STATISTICAL DESIGN & POWER

The overall project has three specific aims. This application relates to Aim 2, where which entails human subjects research.

Aim 2: Conduct a hypothesis driven pilot test of the TLC intervention with dementia caregivers

Statistical Design & Power - Aim 2

The purpose of Phase 2 is to conduct a fully-powered pilot study to measure feasibility and efficacy of the TLC intervention with a sample of dementia caregivers (n=120). This section describes the planned analyses to assess efficacy of the TLC intervention.

Study Design

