When substituting the Mediator M in equation 3 the indirect pathway by which the TLC intervention impacts wellbeing through time-use is represented by the product of coefficients $a \cdot b$. If significant, then mediation is present. If the direct pathway c in equation 3 becomes non-significant in equation 4 (c') when conditioning on the indirect pathway, then M is said to fully mediate the relationship between TLC and wellbeing. Importantly, in the models we will control for individual values of the wellbeing outcomes obtained before the start of the TLC intervention. The indirect pathway will be tested using the Sobel test that divides product-of-coefficients $a \cdot b$ by the first-order delta-method standard error of the indirect effect. This value is compared against a standard normal distribution to test for significance.¹⁴⁸ We will also consider additional statistical mediation tests that account for non-normality of the product of coefficients and/or bootstrapping methods for more accurate estimates.¹²¹

Although not stated as distinct hypotheses, we will conduct additional exploratory analyses to further explain for whom and how the intervention achieves its effect. These analyses will be guided by the following questions: Do variations in the receipt of the intervention modify these relationships? For example, do participants that report higher intervention feasibility (i.e., higher satisfaction and usability of the tool) or higher dosage (i.e., they accessed more of the intervention's features) show stronger treatment effects? This will be assessed by replacing the dichotomous intervention variable X (TLC vs. WLC) in equation 1 with measures indicating dosage or perceived feasibility. Similarly, we will explore whether individual characteristics or circumstances modify the relationship between intervention, time-use satisfaction, and wellbeing over time. Here, we will use biologic variables of gender and age as well as measures that capture changes in the context of the caregiving relationship as both control variables and interaction. Finally, we will explore whether treatment effects maintain, attenuate, or no-change once the intervention period ends. This will be assessed using a repeated-measures design using Group A's data from immediately post-intervention through the 8-week follow-up period.

Power and Sample Size

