We assume clinically relevant small to medium effect sizes in the main outcomes of interest corresponding to 4-6.5 mean change on the total "caregiver burden" outcome and 1.0-1.4 mean change on the "anxiety" outcome. Power and sensitivity analysis were computed in GPower using RMANOVA finding a total sample of 116 would be sufficient to achieve

power of greater than 90% to detect these effect sizes. Therefore, we will aim to have a final sample size of 120 (60 in each sequence) with a 25% over-recruitment to account for study attrition providing a total sample size of 150.

Sample size and sensitivity analyses for mediation analyses are based on empirical estimates conducted by Fritz and MacKinnon (2007).¹²¹ Assuming medium effects for each of the two parts of the indirect pathways (i.e. TLC->Time-use and Time-use->Wellbeing) in Figure 3, a sample size of 75-120 will provide greater than 80% Power (Sobel148 medium-medium effects) at $p=0.05$.

Missing Data

We will explore missing data patterns in SPSS using the Missing Value Analysis tool. We will specify the pattern fixed effects and interactions utilizing Little's test for Missing Completely at Random. In keeping with an intent-to-treat standard and assuming maximum likelihood estimation, we will use all available data for analyses. It is not necessary to eliminate observations from participants who subsequently drop out, nor is it necessary to impute individual observations. Both practices can bias estimation and distort variability. The maximum likelihood estimates given the observed data points are the values most likely to have generated the complete ensemble of observed sample data under the assumed model. Systematic missingness (as determined by missing data patterns) may be included in our mixed effects model. Potentially non-ignorable missing data will be investigated using multiple imputation sensitivity analyses under a diverse set of covariate predictors. To minimize loss of scale scores due to missing items in a computed scale, we will prorate the respondent's score based on available items. If a respondent is missing more than 30% of the items in a computed score for the primary outcome variables, we will code the scale score as missing.

Note: feasibility is another primary outcome of the pilot test. Feasibility-related analyses are discussed at the end of this document, since the focus on feasibility and the analytic strategies to measure feasibility are shared across Aims 1, 2, and 3.

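### The H4 "full mediation" label compares c and c' from fits that can use different person-intervals, because satisfaction exists only where respite was taken and rated

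*Combined protocol and SAP*

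**What the plan says.** All references are to the combined protocol and SAP.

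- **H4.** Equation 2 regresses the mediator on intervention, equation 3 regresses wellbeing on intervention without the mediator, and equation 4 adds the mediator. Mediation counts as present if the product a*b is significant: "The indirect pathway will be tested using the Sobel test". A second rule then grades it. If c "becomes non-significant in equation 4", where it is written c', the mediator is labelled as fully mediating the relationship.
- **Self-administered questionnaires and daily EMAs.** Caregivers complete a daily assessment "in which they indicate if they used respite that day, and if so, their experienced and evaluative satisfaction with respite time-use". H2 repeats the skip pattern and averages the ratings over the four-week intervals between surveys.
- **Study Design.** Burden and anxiety are surveyed at T0 and every four weeks to T20, with no condition on respite use.
- **Inclusion Criteria.** The caregiver must "have access to and/or interest in using respite at least once a week", so interest without current use is enough to enter.
- **Missing Data.** Under maximum likelihood, "we will use all available data for analyses", and imputing individual observations is called unnecessary. Multiple imputation appears only as a sensitivity analysis and does not name the mediator.

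Nothing in the document says what happens to an interval without rated respite, or requires equations 3 and 4 to use the same rows.

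**The concern.** A four-week interval with no rated respite day has an outcome but no mediator value. Maximum likelihood in a mixed model for the outcome copes with missing outcomes. It does not keep a row whose predictor is missing unless the predictor is modelled too. Under the all-available-data rule, equation 3 would therefore use every survey, and equation 4 only those surveys whose interval has a satisfaction mean.

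The move from c to c' then mixes two things: conditioning on the mediator, and changing the sample. An effect can lose significance between the two fits because rows went missing, and this would be read as evidence that the direct path has vanished. At stake are the full-mediation label and any statement about how much of the total effect remains direct.

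**Working it through.** **1. The plan's own figures.** Recruitment: 120 x 1.25 = 150, which agrees. For mediation, Power and Sample Size gives 75-120 for more than 80% power with medium-medium effects, but puts no number on medium. With a = b = 0.39, simulated Sobel power is 0.66 at 75, 0.79 at 90, 0.86 at 100 and 0.94 at 120. Smaller readings of medium give 0.51 to 0.71 at 120. The range can be neither confirmed nor refuted. The section makes no stated allowance for intervals without a mediator value.

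**2. Rows in each fit under the plan as written.**

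| Fit | Needs | Interval without rated respite |
|---|---|---|
| Equation 2 (a) | mediator | dropped |
| Equation 3 (c) | outcome | kept |
| Equation 4 (c', b) | outcome and mediator | dropped |

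The product a*b comes from equations 2 and 4, which lose the same no-respite intervals. The comparison of c with c' uses equations 3 and 4, which do not match. In least-squares fits with the same covariates, c - c' = a*b holds exactly on common rows and need not hold otherwise. In multilevel fits the equality is approximate even on common rows.

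**3. Row loss alone.** If information is proportional to rows, the expected z scales with the square root of the share kept. With 20% lost, z = 2.0 becomes 2.0 x sqrt(0.8) = 1.79, below 1.96. An effect with 90% power has expected z 3.24, which becomes 3.24 x sqrt(0.8) = 2.90, so the risk is much smaller at the planned power.

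**4. Mediator does nothing (b = 0), c/c' rule taken alone.** Assumptions: N = 120, direct effect 0.592 SD (90% power for c), a = 0, rows lost at random, two-sided 0.05.

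| Rows lost | c significant on all rows, c' not | c and c' on common rows |
|---|---|---|
| 0% | 0.6% | 0.4% |
| 10% | 4.8% | 1.0% |
| 20% | 9.8% | 1.3% |
| 30% | 14.8% | 1.2% |
| 40% | 21.7% | 1.8% |

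Fitting the kept rows without the mediator already gives 4.4 / 9.4 / 14.3 / 21.0%, so row loss is the cause. A six-wave random-intercept model with about 76% power for c shows the same: 2.0% with no loss, then 7.7 / 14.5 / 18.1 / 28.1%, against about 2% on common rows.

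**5. Mediator does nothing, with the plan's Sobel test also required.** With b = 0 and a = 0, 0.5 or 0.78, the pattern of a*b significant, c significant and c' not significant occurs in at most 0.6% of trials at 0-40% loss, with no clear rise as loss grows.

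**6. Partial mediation, Sobel test required.** Here a = 0.78, b = 0.39 and the direct effect is 0.592, so the full-mediation label is wrong. With no rows lost it is still given in 14.4% of trials.

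| Rows lost | c on all rows | c on common rows | Due to mismatch | Remaining rise over 14.4% |
|---|---|---|---|---|
| 10% | 17.3% | 16.9% | 0.4 points | 2.5 points |
| 20% | 22.4% | 21.6% | 0.8 points | 7.2 points |
| 30% | 25.8% | 23.8% | 2.0 points | 9.4 points |
| 40% | 28.2% | 25.3% | 2.9 points | 10.9 points |

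The mismatch column is the first percentage minus the second; the last column is the second minus 14.4. The mismatch matters more when the direct effect is smaller and c lies nearer the significance threshold. Over the partial-mediation settings tried, it added roughly 0 to 9 points at 10-30% loss, and up to 13 at 40%.

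**The case against.** A reader might infer that this flaw lets the trial report mediation when the mediator does nothing. The documents do not support that. The plan decides presence by a*b, whose two components lose the same no-respite intervals, and step 5 shows that a false full-mediation finding is then very rare. The percentages in step 4 describe a rule that the plan does not use on its own.

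Four further objections deserve weight.

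- **Row deletion is inferred.** The plan allows systematic missingness to enter the mixed model, promises multiple-imputation sensitivity analyses, presents equations 2-4 as the simplest form, and cites longitudinal mediation methods that cannot be seen here. A joint model would keep the rows. This stands as a limit, but no such model is specified.
- **The share lost is unknown.** A mean is absent only if no respite day was rated in about 28 days, and entrants have access to, or interest in, weekly respite. Interest-only entry makes some loss plausible without sizing it. The completion benchmark of at least 80% measures response, not respite use.
- **Common rows do little for the error rate at the planned effect size.** In step 6 most of the rise comes from c' losing precision, and the label is wrong in 14.4% of trials with no loss at all. This stands: the change-in-significance rule is a weakness in its own right.
- **Common-row c departs from intent to treat.** It conditions on respite use after randomisation. This also stands and limits how that estimate may be presented.

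**Conclusion.** The point holds in a narrow form. As written, the plan compares c and c' across fits that can rest on different person-intervals, so the comparison is not like for like and c - c' need not equal a*b. The finding that mediation is present is untouched. What is affected is the full-mediation label and the direct-versus-total comparison, a minor matter within H4.

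The size is roughly 0 to 9 percentage points added to the label under partial mediation. This assumes that 10-30% of rows are lost, that loss is random, and that no joint model is fitted; none of these is settled by the documents. If the intervention changes respite use, the kept rows are selected after randomisation, and c' could also be biased in either direction; that is not in the figures. If T0 has no preceding EMA interval, equation 4 could lose that row as well.

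**What to change.** Add to H4 that equations 2, 3 and 4 are fitted on the same person-intervals, namely those with both a satisfaction mean and the outcome. Report c, c' and a*b with confidence intervals on that set, and let these carry the interpretation rather than the change in significance alone. Show the all-rows c beside them as the H1 intent-to-treat estimate. State the rule for intervals without rated respite, and report the number of person-intervals excluded in each group.

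The cost is a few sentences in the SAP and one extra fit of equation 3; no new data are needed. The downside is that the common-row c is conditional on post-randomisation respite use and may differ from the H1 estimate, so it should be presented only as the comparator for c'. The change makes the comparison coherent but does not recover the precision that c' loses with the dropped intervals.
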